3.5.6 Pharmacodynamic Per-Protocol Set

The Pharmacodynamic Per-Protocol Set (PD-PPS) is a subset of the SS, consisting of those participants who had no important protocol deviation affecting the serum concentrations of total IgG, IgG subclasses, or neurofilament light chain. Post-Baseline deviations will not necessarily lead to total exclusion of a participant from the PD-PPS but may lead to exclusion of specific data.

3.6 Treatment assignment and treatment groups

All study participants will receive rozanolixizumab in the OLE.

Analyses will be performed by treatment group and for all study participants where stated. The treatment groups will be displayed as follows in the TFLs:

- Treatment group 1: Newly treated (ie, study participants treated with placebo in parent study)
- Treatment group 2: Previously treated (ie, study participants treated with rozanolixizumab in parent study)

Participants with the reduced dose due to tolerability issues will be mapped under the same treatment groups. These study participants will be flagged in the listings. For the Observation period the same treatment groups will be displayed.

It is expected that study participants will have received treatment as randomized in CIDP01 and hence safety and efficacy analyses will be based on the randomized treatment group in CIDP01. However, if after unblinding of CIDP01 it is determined that a study participant has received

treatment different to the treatment they were randomized to, then for safety analyses the study participant will be allocated according to the actual treatment they received.

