The neonatal major histocompatibility complex-class-I-like FcRn recycles immunoglobulin G (IgG) and albumin from most cells and transports it bi-directionally across epithelial barriers to affect systemic and mucosal immunity. It has been shown that FcRn rescues both IgG and albumin from intracellular lysosomal degradation by recycling it from the sorting endosome to the cell surface (Anderson et al, 2006). Immunoglobulin G has a half-life of approximately 3 weeks in man. This is achieved by interaction of IgG with the receptor, FcRn. Thus in effect FcRn salvages IgG, and blockade of FcRn accelerates removal of endogenous IgG.

Rozanolixizumab is a humanized anti-FcRn monoclonal antibody that has been specifically designed to inhibit IgG binding to FcRn without inhibiting albumin binding to FcRn.

Rozanolixizumab is being developed as an inhibitor of FcRn activity with the aim to reduce the concentration of pathogenic IgG in patients with IgG auto-antibody mediated diseases.

Rozanolixizumab was derived from a rat antibody with specificity for human FcRn. To date, rozanolixizumab has been administered to healthy study participants in a completed first-in-human (FIH) study (UP0018), a completed Phase 2 study in study participants with primary immune thrombocytopenia (ITP) (TP0001, evaluating [REDACTED] by sc route across 5 cohorts), and a completed Phase 2 study in study participants with myasthenia gravis (MG) (MG0002, evaluating [REDACTED] by sc route).

Additional information on the development of rozanolixizumab can be found in the current version of the Investigator's Brochure (IB) for rozanolixizumab.

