5 STUDY DESIGN

5.1 Study description

This is a Phase 2A, multicenter, single-arm, OLE study to evaluate the safety, tolerability, and efficacy of rozanolixizumab during long-term treatment of study participants with CIDP from a previous study with rozanolixizumab.

Access to CIDP04 for study participants coming from CIDP01: Study participants from CIDP01 who have completed the Treatment Period (ie, all visits up to Visit 17) without a relapse of CIDP will be offered the opportunity to be directly enrolled into this OLE study. Study participants will enter CIDP04 on the same day as the last study visit in CIDP01: Visit 17. Study participants from CIDP01 who have experienced a relapse of CIDP (during either the Treatment Period or the Observation Period), have been successfully rescued and stabilized with SOC medication and have consented to enter this OLE study, may be assessed for eligibility. The study participants who relapsed during the Treatment Period of CIDP01 will be offered entry into CIDP04 only once CIDP01 study results are available, after the blind has been broken at the end of the study, and it is confirmed they received placebo in CIDP01.

In case the study participants have a gap period between the end of the parent study and the start of this OLE study (ie, last visit in the parent study does not take place on the same day as entry of study CIDP04), a Screening Period of 2 to 5 weeks will be applicable to confirm that the study participant still meets the eligibility criteria for entry in the OLE study and allow for a smooth transition between the treatment used by the study participants during the gap period and the initiation of rozanolixizumab. The CIDP04 study includes a first 24-week Treatment Period (Part 1) followed by a second Treatment Period (Part 2) of up to 52 weeks (or until an Access Program or equivalent is in place, whichever comes first). Entry to the Treatment Period (Part 2) will be contingent to a favorable individual benefit-risk after careful individual assessment has been performed for each study participant completing Treatment Period (Part 1). An 8-week Observation Period will be followed in case of premature termination or after completion of the Treatment Periods (either at end of Part 1 for study participants not continuing in Part 2 or at end

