6 SELECTION AND WITHDRAWAL OF STUDY PARTICIPANTS

6.1 Inclusion criteria

To be eligible to participate in this study, all of the following criteria must be met:

1. An Institutional Review Board (IRB)/Independent Ethics Committee (IEC)-approved written Informed Consent form (ICF) is signed and dated by the study participant.
2. Study participant who has completed one of the previous rozanolixizumab study(ies) that allow access to the present study.

For example, for study participants coming from CIDP01 the following criteria will have to be met:

- Study participant has completed the Treatment Period of the parent study with no relapse of CIDP disease and has chosen to enter this OLE study directly upon completion of the Treatment Period of the parent study, or
- Study participant has experienced a relapse of CIDP during the parent study (either during the Treatment Period or the treatment free Observation Period), has been successfully rescued and stabilized with eg, IVIg based on assessment of the investigator (maximum of 3 months of stabilization treatment), and has chosen to enter this OLE study. Study participants who already relapsed during the Treatment Period of CIDP01 must have been assigned to placebo treatment during that period in order to be able to qualify for enrollment into CIDP04.

3. The study participant is considered reliable and capable of adhering to the protocol visit schedule, or medication intake according to the judgment of the investigator, and has been compliant with the parent study assessments.
4. Female study participants of child-bearing potential must have the results of a negative serum pregnancy test from either the parent study (not older than 5 weeks) or the Screening Visit available at the CIDP04 Baseline (Visit 2), and a urine pregnancy test must be negative when study participant enters CIDP04 and prior to further dosing at each study visit thereafter.

Female study participants of childbearing potential must agree to use a highly effective method of birth control, during the study and for a period of 3 months after their final dose of IMP. Highly effective forms of birth control are methods that achieve a failure rate of less than 1% per year when used consistently and correctly. According to the International Council for Harmonisation (ICH) M3 R2, highly effective methods of birth control include:

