6. For study participants entering CIDP04 after a gap period since the parent study: Study participant is on a stable dosage (not more than $\pm 20\%$ deviation) for SC Ig or IV Ig and a fixed interval (eg, once weekly ± 2 days for SC Ig or every 2 to 6 weeks ± 5 days IV Ig, respectively) for stability in functioning between dosing.

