4.9 Examination of subgroups

Not applicable.

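### The SAP's newly treated group combines two entry routes, so its relapse rate and IgG fall depend on the mix of routes as well as on the drug

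*SAP*

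**What the plan says.** SAP 3.6 sets up two display groups. The first is "Treatment group 1: Newly treated (ie, study participants treated with placebo in parent study"; the second is everyone given rozanolixizumab in the parent study. How a participant entered CIDP04 plays no part in the definition.

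The protocol gives CIDP01 participants two routes. Section 5.1 lets in directly those "who have completed the Treatment Period (ie, all visits up to Visit 17) without a relapse of CIDP will be offered the opportunity" to enrol. Criterion 2 in Section 6.1 also admits a participant who relapsed in CIDP01 and "has been successfully rescued and stabilized with eg, IVIg based on assessment of the investigator (maximum of 3 months of stabilization treatment". Anyone who relapsed during the CIDP01 Treatment Period "must have been assigned to placebo treatment during that period in order to be able to qualify for enrollment into CIDP04", so all of these participants fall in the newly treated group.

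Criterion 6 adds: "For study participants entering CIDP04 after a gap period since the parent study: Study participant is on a stable dosage", "for SC Ig or IV Ig and a fixed interval". Exclusion criterion 18 removes gap entrants averaging under 0.4 g IgG/kg/month, and Section 7.8.2 prohibits Ig during treatment.

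Relapse is tabulated by treatment group and in total (SAP 8.1.2), and total IgG by treatment group, timepoint and ADA status (SAP 9.2.1). The section headed "4.9 Examination of subgroups" is marked not applicable, as is covariate adjustment (SAP 4.1). Prior Ig appears only in a listing (SAP 6.2).

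**The concern.** The two kinds of newly treated participant differ in ways that bear directly on both outcomes. A direct entrant has just been through an 11-week placebo period without relapsing, so staying relapse-free in CIDP04 is weak evidence about the drug. A gap entrant has a relapse on record and gives up Ig on starting rozanolixizumab, so staying relapse-free is much more informative. For IgG, a gap entrant's Visit 2 sample contains infused IgG that will decay whether or not the drug works.

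The mix is also partly a matter of logistics. Treatment Period relapsers can enter only after CIDP01 has been unblinded, with at most 3 months of stabilization treatment allowed, so their number depends on study timing as well as on how patients respond.

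At stake is how to read the study's only data from participants starting rozanolixizumab for the first time. Long-term efficacy is the secondary objective, and these descriptive displays are the evidence for it. A pooled rate shows neither whether the drug can take the place of Ig nor whether stable patients stay stable.

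**Working it through.** The documents state no relapse rate, IgG figure or sample size for CIDP04, so there is no plan figure to reproduce. The calculations below are illustrations.

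**Relapse.** Let w be the share of direct entrants. Pooled rate = w × p(direct) + (1 − w) × p(gap). Assumed risks, not in the documents: 5-10% direct, 40-60% gap, held fixed.
- w = 0.8: 0.8 × 5% + 0.2 × 40% = 12%; 0.8 × 10% + 0.2 × 60% = 20%.
- w = 0.2: 0.2 × 5% + 0.8 × 40% = 33%; 0.2 × 10% + 0.8 × 60% = 50%.

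The pooled rate moves from 12-20% to 33-50% with no change in what the drug does. The converse also holds. Assume 10% and 80% with no drug effect and w = 0.80: 8% + 16% = 24%. Halve both risks and set w = 0.46: 0.46 × 5% + 0.54 × 40% = 24%. The same pooled rate fits no effect and a halving of risk.

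**Total IgG in gap entrants.** Protocol Section 2 supplies the decay rate: "Immunoglobulin G has a half-life of approximately 3 weeks in man". Week 9 is 8 weeks after Visit 2. Of the infused IgG present at Visit 2, the fraction gone by then is 1 − 2^(−8/3) = 0.84.
- Assume 20-50% of Baseline IgG is infused. With no drug effect, the fall from washout is 0.20 × 0.84 = 17 points to 0.50 × 0.84 = 42 points.
- Assume the drug lowers whatever IgG would otherwise be present by 60%. The total fall is 1 − 0.4 × (1 − share × 0.84), so washout adds 0.4 × 17 = 7 points to 0.4 × 42 = 17 points beyond the drug's 60%.

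**Is a 20-50% infused share plausible?** Mean steady-state increment = dose rate / (k × V). Take the minimum dose of 0.4 g/kg per 30 days, k = ln 2 / 21 = 0.033 per day, and assumed V = 0.07-0.10 L/kg. This gives 5.8 to 4.0 g/L. Against an assumed 7-12 g/L of endogenous IgG, the share is 4.0/16.0 = 25% to 5.8/12.8 = 45%. Late sampling within an IVIg interval would lower it; doses above the minimum would raise it.

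**Direct entrants for comparison.** After an assumed 12 weeks off Ig, 2^(−12/3) = 6% of infused IgG remains. With the minimum dose and the same V and endogenous IgG, the Week 24 fall without drug is about 2-5% in direct and 25-45% in gap entrants. At an assumed 60% drug effect it is about 61-62% and 70-78%, a difference of about 9-16 points.

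**Baseline rule.** The contrast assumes Visit 2 as Baseline for both routes, as SAP 3.3 says for placebo participants. SAP 2.2 and Protocol Section 4 instead give all direct entrants the parent-study Baseline. CIDP01 enrolled people maintained on an Ig-dependent regimen, so under that rule direct entrants' Baseline may also carry infused IgG and the contrast could shrink.

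**The case against.** CIDP04 is a single-arm safety study. Its efficacy summaries are descriptive, it has no sample size calculation, and efficacy against placebo is CIDP01's randomized question. Prior Ig is listed with a flag for parent-study rescue, and visit dates are listed, so a reader could rebuild the split by hand. The relapse risks and the mix are assumed, and the relapse arithmetic shows only that an average depends on its weights. Extra columns may leave cells too small to summarize.

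Much of this stands as a limit on size. It does not remove the problem: the pooled figures are what the report will present, and a listing does not replace a prespecified table. SAP 3.1 already has a rule for cells with fewer than 3 participants. The SAP also already uses the needed information: gap status defines prior medication (SAP 6.4.1), and Observation Period TEAEs are stratified by Ig use (SAP 10.2).

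Four stronger readings are tempting but unsupported:
- A reader might infer that the results reflect the mix instead of the drug. They reflect both; at an assumed 60% effect the drug accounts for most of the percentage IgG fall.
- A reader might take 17-42 points as the distortion. That range applies only at zero drug effect, and every participant receives the drug.
- A reader might extend the point to vaccine titres. Table 3-1 sets that Baseline for placebo participants at Screening, which direct entrants do not have, and the Visit 2 procedures include no titre sample. Change in titre would therefore come from gap entrants alone, which is a different issue.
- A reader might conclude that direct entrants were stable without Ig throughout CIDP01. That is an inference; CIDP01's concomitant-treatment rules are not in these documents.

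**Conclusion.** The point holds. The newly treated group combines two populations with different relapse histories and different Ig status at entry, and no planned table separates them. Its pooled relapse rate and percentage IgG fall cannot be interpreted without knowing the mix. The illustrated sizes are a shift in pooled relapse from 12-20% to 33-50% over direct shares of 80% to 20%, and about 7-17 points of extra Week 9 IgG fall in gap entrants. Both rest on assumed risks, mix, infused share and drug effect; the documents supply only the half-life and the minimum Ig dose. The IgG contrast also depends on which Baseline rule applies to direct placebo entrants.

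The previously treated group is mixed too. It holds direct completers and any participants who relapsed in the Observation Period, but not those who relapsed on rozanolixizumab, so a comparison between the two groups is affected as well. The change should be made; it does not put the primary safety objective in doubt.

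**What to change.** In SAP 3.6 and 4.9, add entry route (direct versus after a gap) as a display split within each treatment group, with n per cell and the pooled column kept. Apply it to relapse, time to relapse, rescue use, change in iRODS, adjusted INCAT and grip strength, and total IgG. Leave vaccine titres out. State that efficacy and IgG conclusions about drug-naive participants will rest on the split figures.

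Reconcile SAP 2.2 with SAP 3.3 so that direct placebo entrants have one Baseline definition, and record any departure from Protocol Section 4 in SAP 3.9.

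The cost is SAP wording and extra table columns. Entry route follows from data already recorded, so no new collection is needed. The drawback is small cells, which will be reported under the existing rule in SAP 3.1 and should be described without formal comparison.

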3.7 Center pooling strategy

It is planned to recruit study participants in Europe, United States of America and Canada in this study, with possible extension to other regions and countries. No stratification by site or country will be performed.

3.8 Coding dictionaries

Adverse events (AEs) will be coded using version 23.1 or later of the Medical Dictionary for Regulatory Activities (MedDRA®).

Medications will be coded according to version Sep 2017 or later of the World Health Organization Drug Dictionary (WHODD). Medical procedures will not be coded. If newer dictionary versions become available, data will be coded according to the approved internal standard dictionary management processes.

3.9 Changes to protocol-defined analyses

- CIDP relapse (maximum grip strength as assessed by site personnel) is defined as a clinically important deterioration from Baseline in grip strength as measured by site personnel, ie, a decline of $>14\text{kPa}$. Additionally, relapses defined by decline of $>8\text{kPa}$ will be investigated.
- The FAS definition is clarified to include at least one valid post baseline iRODS assessment result.
- The PD-PPS will be handled as a subset of the SS instead of the FAS as defined in the protocol to not exclude data due to missing efficacy results.
- To prevent bias in efficacy evaluation, an efficacy assessment is considered invalid, if that assessment follows the first intake of rescue medication. Assessments on the same day as first intake of rescue medication are considered valid.
- The MFAS is included as an additional analysis set in the SAP and was not part of the final clinical study protocol (CSP). This was added as a sensitivity analysis, to ensure the robustness of the efficacy results in relation to dose variation.
- Elevated liver function tests and potential drug induced liver injury criteria are harmonized across the rozanolixizumab program. Protocol-defined criteria are updated to match UCB's standard evaluations. Please refer to Section 10.3.1 for a list of the criteria that will be evaluated.

$\geq 3\times\text{ULN}$ ALT or AST with coexisting $\geq 2\times\text{ULN}$ total bilirubin in the absence of $\geq 2\times\text{ULN}$ ALP

will instead be defined as

(ALT or AST increase $\geq 3\times\text{ULN}$) and Total bilirubin $\geq 2\times\text{ULN}$ and ALP $<2\times\text{ULN}$ to match program standards and general medical definitions.

- The study variable “Change in CIDP-specific auto-antibody levels in serum from Baseline during Treatment and Observation Periods” will not be analyzed in scope of this SAP.

Sampling dates are captured in the CRF and will be listed. The samples’ results will not be part of this study’s database and instead analyzed and reported separately. The same is true for exploratory biomarkers RNA, proteins and metabolites variables.

3.9.1 Changes related to COVID-19

3.9.2 With the event of the COVID-19 pandemic, an additional protocol deviation category (related/not related to COVID-19) has been introduced as well as an eCRF page "COVID-19 Impact" to identify visits and procedures which may have been impacted. These will be presented in the analysis results as described in Section 5.2. Interim Analysis

Per protocol section 14.7:

“Two interim analyses will be conducted. Firstly at the time of the lock of the parent study CIPD01 and additionally once all study participants have completed Part 1 of the Treatment Period in CIDP04 and have either entered into the Treatment Period Part 2 or the Observation Period. Details of the planned analyses will be fully outlined in the respective SAPs.”

The events "lock of the parent study" and "all study participants have completed Part 1 of the Treatment Period in CIDP04" are expected to be close together and not differ enough in presented data to provide benefit by additional analysis. Therefore, these two interim analyses will not be performed.

4 STATISTICAL/ANALYTICAL ISSUES

4.1 Adjustments for covariates

Not applicable.

4.2 Handling of dropouts or missing data

4.2.1 Efficacy data

For study participants who prematurely withdraw for any reason before Visit 26, data collected during the PEOT Visit will be mapped to the closest missing visit according to the visit schedule utilizing the relative day in study to a maximum of Visit 26 (end of treatment period). However, if a participant receives rescue medication prior to the PEOT visit, any efficacy assessment post intake will be regarded invalid and only listed. Assessments on the same day as first intake of rescue medication are acceptable for analysis.

Study participants administered an Ig infusion rescue medication during the treatment phase will be considered relapsed even in case no relapse was documented. Missing relapse data, i.e. data for any relapse event definition, will be considered missing. In case of drop-out, if no relapse occurs or rescue medication is taken until PEOT visit (inclusively), the subject will be censored for time-to-event analysis at the date of PEOT visit.

Participants are asked to record three grip strength score assessments at each day. The efficacy parameter will be derived from grip strength scores taken by a participant up to five days prior to the first IMP (for Baseline value) or visit date (for post Baseline visit value):

1. Maximum of grip strength assessments available at a particular day
2. Mean of maximum grip strength over most recent three non-missing days - up to a maximum of five days
3. Missing values: In case all three assessments of a day are missing, the maximum grip strength score will be set to missing and will not be used for the derived score. In this case the preceding day's maximum grip strength score will be used instead, but no later than the fifth day prior to the first IMP or visit date respectively. In case data is entirely missing during the last five days prior to the visit, the derived score will be set to missing.

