3.2 General study level definitions

3.2.1 Analysis time points

3.2.1.1 Relative day

Relative day for an event will be derived with the date of the first sc infusion of IMP as reference. For study participants treated with rozanolixizumab in parent study (eg CIDP01) the date of the first sc infusion of IMP administered at the parent study will be used as reference and be considered as the date of the first intake of IMP. For study participants treated with placebo during the parent study, date of first intake of IMP will be date of first IMP in CIDP04.

Relative days for an event of measurement occurring before the date of first sc infusion are calculated as follows:

$$\text{Relative Day} = [(\text{Event Date} - \text{Date of First Infusion})]$$

For events or measurements occurring before the date of the first sc infusion, relative day will be prefixed with '-' in the data listings.

The relative day for an event or measurement occurring on or after the reference date to the date of the last infusion is calculated as follows:

$$\text{Relative Day} = [(\text{Event Date} - \text{Date of First Infusion}) + 1]$$

For events or measurements occurring after the date of the last sc infusion, relative day will be prefixed with '+' in the data listings. Relative day will be calculated as follows:

$$\text{Relative Day} = + [(\text{Event Date} - \text{Date of Last Infusion})]$$

There is no relative Day 0. Relative day is not calculated for partial dates in cases where relative day is shown in a study participant data listing. In such cases, relative day should be presented as '---' in the study participant data listings.

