3.3 Definition of Baseline values

For all study variables, the Baseline values for study participants treated with rozanolixizumab in the parent study (ie, CIDP01) will be the Baseline values from the parent study. For study participants treated with placebo in the parent study, the Baseline values will be the ones present at Baseline in CIDP04 (Visit 2 or if missing, the Screening Visit value (if applicable)). Note this Visit 2 value may be corresponding to the last value registered into CIDP01 as these may be the same visit.

Scheduled or unscheduled measurements can be used as the Baseline value. Expected measurement-specific Baseline timepoints are presented in [Table 3-1](#). If an unscheduled measurement occurs after the planned baseline measurement timepoint but before dosing, then the unscheduled measurement will be used as the baseline value.

Table 3–1: Expected Baseline

Measurement	Definition of Baseline
Safety data: 
• Safety Lab (Clinical chemistry, Hematology, Urinalysis)• ECG• Vital signs• Total protein, albumin, α- and β-globulins	For study participants treated with rozanolixizumab in parent study CIDP01: Safety labs, vital signs, total protein, albumin, α - and β -globulin: Baseline visit (Day 1) of parent study, if missing Screening visit of parent study (pre-dose value, if applicable). For study participants treated with placebo in the parent study: Safety labs, vital signs, total protein, albumin, α - and β -globulin: Baseline visit (Day 1) in CIDP04, if missing Screening visit (if applicable) (pre-dose value, if applicable). ECG: mean of triplicate values of Baseline visit (Day 1) in CIDP04. If missing Baseline visit, mean of triplicate values of Screening visit (if applicable).
Efficacy data 
• iRODS• INCAT• Grip strength (assessed by site personnel)• RT-MRC and original MRC• Fatigue score• CIDP PRO• PGIS• PGIC	For study participants treated with rozanolixizumab in parent study CIDP01: Baseline visit (Day 1) in CIDP01, if missing Screening visit For study participants treated with placebo in the parent study: Baseline visit (Day 1) in CIDP04, if missing Screening visit (where applicable)

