4.3 Handling of measurements obtained at the premature end of treatment visit

Study participants who withdraw from the study prematurely will be encouraged to return for the PEOT visit. The following rules will apply with regard to the inclusion of the results obtained at the PEOT in the descriptive summaries:

- Any measurements (safety, immunological and PD assessments) conducted at the PEOT should be included in the summaries for the respective scheduled visit, if the PEOT occurs at the time of the next scheduled visit (within the tolerance window specified in the protocol);
- If the PEOT does not correspond to the day of a scheduled visit, the safety and other relevant assessments of the PEOT should be mapped to the nearest scheduled visit, relative to the Baseline visit date, following the last scheduled visit where assessments are available;
- If the date of the PEOT is equidistant between 2 scheduled visits at which no scheduled assessments were performed, the assessments from the PEOT will be mapped to the earliest of these visits.

Different domains from the same PEOT may be re-assigned to different study visits depending on the study schedule of assessments, ie, measurements obtained at the PEOT can only be mapped to a scheduled visit at which the respective assessment was intended to be measured. Assessments from the PEOT that are mapped to scheduled visits will be flagged in the data listings.

Visits after the PEOT following the schedule of the 8-Weeks Observation period, will be mapped to the corresponding planned visit. Assessments on these visits will be flagged in the data listing.

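### The day count that places efficacy results from the premature end of treatment (PEOT) visit is not anchored to the CIDP04 schedule, so those results can be filed under the wrong week.

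*SAP*

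**What the plan says.** **Efficacy (SAP 4.2.1).** PEOT data are "mapped to the closest missing visit according to the visit schedule utilizing the relative day in study", with Visit 26 as the latest visit allowed. The phrase is not defined in that section, and no rule is given for ties.

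**Relative day (SAP 3.2.1.1).** The reference is the first infusion. For participants given rozanolixizumab in CIDP01, "the date of the first sc infusion of IMP administered at the parent study will be used as reference". For those given placebo, "date of first intake of IMP will be date of first IMP in CIDP04". The first-infusion formula (event date minus first infusion, plus 1) is restricted to events "occurring on or after the reference date to the date of the last infusion is calculated as follows". The section then adds: "For events or measurements occurring after the date of the last sc infusion", relative day is the event date minus the date of the last infusion.

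**Other domains (SAP 4.3).** A PEOT within the protocol window of the next scheduled visit goes to that visit. Otherwise safety and other relevant data "should be mapped to the nearest scheduled visit, relative to the Baseline visit date", moving only forward from the last scheduled visit that has assessments.

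**Baseline (SAP 3.3 and Table 3-1).** For previously treated participants, Baseline values "will be the Baseline values from the parent study", and Table 3-1 points to the Day 1 Baseline visit of that study. Yet Protocol 8.2.1 and SAP 6.1 also call CIDP04 Visit 2 the Baseline visit.

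**Cap (SAP 3.2.1.2).** Visit 26 is Week 25 for participants in Part 1 only and Week 77 for those who also complete Part 2.

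**The concern.** A visit schedule can only be matched to a day count that starts where the schedule starts. Here the schedule starts at the first CIDP04 dose. Newly treated participants have a first-infusion count that starts there; previously treated participants have one that starts in CIDP01, at least 11 weeks earlier. The last-infusion count restarts near zero at the end of treatment and says nothing about how far into CIDP04 a participant had come.

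The by-visit summaries of iRODS, adjusted INCAT, grip strength and RT-MRC are presented by treatment group. Relapse or rescue during treatment requires stopping the study drug (Protocol 6.4 and 7.8.3), so some PEOT values will come from participants doing badly. If those values move to a later column in one group, or back to an early one in either, the columns no longer show what happened in the week they name. The two PEOT rules also differ in direction, because SAP 4.2.1 lets a result move back to a missed visit and SAP 4.3 does not. iRODS and IgG from one PEOT could therefore appear under different weeks.

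**Working it through.** **Inputs**
- CIDP01 Treatment Period: 11 weeks (Protocol 2). This agrees with the stated CIDP01 durations: 5 + 11 + 12 = 28 weeks and 5 + 11 + 24 = 40 weeks.
- Direct entrants start CIDP04 on the day of CIDP01 Visit 17 (Protocol 5.1), so the offset is taken as 11 × 7 = 77 days. The exact day of Visit 17 is not given; 84 and 91 days are shown as a range.
- Part 1 efficacy visits: Weeks 1, 2, 3, 4, 5, 7, 9, 13, 17, 21 and 25 (Protocol Table 5-1 and 8.2). Scheduled day = 7 × (week − 1) + 1.
- PEOT follows the last dose: SAP 3.2.1.2 places Visit 26/PEOT after it, and Protocol Table 11-1 calls Visit 26 nondosing.

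**Assumptions.** PEOT falls in one of Weeks 2 to 24 (23 possibilities, equally weighted, since the documents give no distribution of stop times). No earlier visit was missed unless stated. Part 1 is capped at Week 25. Ties go to the earlier visit, as in SAP 4.3.

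**CIDP04 clock (the reference).** Each PEOT goes to its own visit or the next efficacy visit. Only stops at Weeks 22, 23 and 24 become Week 25: 3 of 23.

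**First-infusion count, offset 77 days.** Day used = CIDP04 day + 77.
- Week 6: 36 + 77 = 113, which is the Week 17 day. CIDP04 clock: Week 7.
- Week 9: 57 + 77 = 134. Week 21 is day 141 (7 away) and Week 17 is day 113 (21 away), so Week 21. CIDP04 clock: Week 9.
- Week 13: 85 + 77 = 162. Week 25 is day 169 (7 away) and Week 21 is day 141 (21 away), so Week 25. CIDP04 clock: Week 13.

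| PEOT in CIDP04 week | Reported at | Weeks late |
|---|---|---|
| 2–4 | 13 | 11, 10, 9 |
| 5–8 | 17 | 12, 11, 10, 9 |
| 9–12 | 21 | 12, 11, 10, 9 |
| 13–16 | 25 | 12, 11, 10, 9 |
| 17–24 | 25 | 8 down to 1 |

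The delays sum to 192, a mean of 192/23 = 8.3 weeks, with a range of 1 to 12. They reach 11 weeks or more in 7 of 23 stop weeks. Stops at Weeks 13 to 24, 12 of 23, are reported as Week 25. Measured against the visit the CIDP04 clock would choose, the mean displacement is 166/23 = 7.2 weeks and it reaches 11 weeks or more in 4 of 23; stops at Weeks 22 to 24 are not displaced.

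Sensitivity:
- Ties at Weeks 4, 8 and 12 sent to the later visit: 13 of 23 at Week 25, maximum delay 13 weeks.
- Offset 84 days: 13 of 23. Offset 91 days: 14 of 23.
- Offset 168 days, an assumed long gap: all 23.
- Part 2, if the cap is Week 77: a PEOT at Week 30 (204 + 77 = 281) is reported at Week 41 (day 281).

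**Last-infusion count.** With PEOT assumed 7 days after the last dose, relative day is +7 for everyone. The closest missing visit on a schedule counted from Day 1 is then simply the earliest missing one. With no missed visit this is the next scheduled visit, the same as the CIDP04 clock. If the Week 3 visit was missed, every PEOT from Week 4 to Week 24 is placed at Week 3.

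**SAP 4.3.** If the Baseline visit date is CIDP01 Day 1, the same 77-day offset enters; if it is CIDP04 Visit 2, the mapping is right. The text supports either.

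**The case against.** The strongest objection is that the last-infusion formula literally governs a PEOT after the final dose. It does not start in CIDP01, is the same in both groups, and gives the right visit when nothing was missed. This stands. A reader might infer from the CIDP01 reference date that every early stop in the previously treated group is certainly reported about 11 weeks or more late, and that the two groups cannot be compared. The documents do not support that: it needs the first-infusion formula to be applied outside its stated range, and even then the cap and rounding to visits give 1 to 12 weeks, with 11 or more in only 7 of 23 stop weeks.

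The formula does not rescue the rule, however. A count since the last dose cannot locate a visit on a schedule counted from the first, and it sends results back whenever an earlier visit is missing. It is also natural to read the day in study as the day in CIDP04, since the schedule and the cap are CIDP04's. That may be what was meant, but the SAP does not say so.

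For SAP 4.3 it is fair that Baseline values and the Baseline visit date are different things, that CIDP04 Visit 2 carries the Baseline label, and that the next-visit window rule correctly places many PEOTs without any day count. The point there is ambiguity, not a demonstrated error.

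Nor do the documents show that most PEOT values come from relapse or intolerance. Access Program entrants also have this visit, and efficacy values after rescue medication are listed only. Having separate rules for efficacy and safety is not in itself wrong.

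**Conclusion.** The point holds as a defect in the mapping rule, to be fixed but not critical. SAP 4.2.1 relies on a day count for which neither available formula is anchored to the CIDP04 schedule in previously treated participants. The first-infusion reading reports Part 1 stops about 1 to 12 weeks late in that group only, with 12 of 23 stop weeks at Week 25 against 3 of 23. The last-infusion reading is correct without missed visits and can place results too early with them, in either group. SAP 4.3 is open to a similar misreading for data outside the next visit's window.

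The sizes rest on a 77-day offset, equal weight for each stop week and ties to the earlier visit. The offset is longer for a previously treated participant who entered after a gap; Protocol 6.1 allows up to 3 months of stabilization.

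A reader might infer that the main safety result or the relapse times are affected. They are not: treatment-emergent adverse events are assigned by date from the first CIDP04 dose (SAP 10.2), and dropouts without relapse or rescue are censored at the actual PEOT date (SAP 4.2.1). The effect is confined to by-visit descriptive summaries, in a study with no formal sample size calculation.

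**What to change.** In SAP 4.2.1 and 4.3:

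1. Map PEOT data for all participants by day in CIDP04: visit date minus date of first CIDP04 dose, plus 1.
2. Allow mapping only to visits after the last attended visit, and only to those where the assessment is planned. SAP 4.3 already works this way; SAP 4.2.1 should match it and adopt its tie rule.
3. State whether the Visit 26 cap is Week 25 or Week 77, including for a participant who enters Part 2 but does not complete it.

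Relative day in SAP 3.2.1.1 can stay as it is for listings. The cost is a few sentences and one derived variable, with no new data and no change to any endpoint.
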